5.7.4 Physical Findings

Not applicable since physical examinations data are not collected in CRF.

5.7.5 Anti-agalsidase alfa Antibody Results

Serum samples will be collected for evaluation of anti-agalsidase alfa antibodies within 6 months prior to the patient receiving the first dose of Replagal and at the biannual or annual safety visits, as applicable. Analysis of anti-agalsidase alfa antibodies will be performed using a validated electrochemiluminescent (ECL) immunoassay following a tiered approach (screening, confirmatory, and titer). Samples that are confirmed positive for the presence of anti-agalsidase alfa antibodies will be further evaluated for the presence of neutralizing antibodies using an enzyme inhibition assay.

Anti-agalsidase alfa antibody data are obtained from 2 different testing schemes. Anti-agalsidase alfa antibody samples collected were initially tested (prior to Nov 2014) following a tiered approach at Shire and results were reported by isotype. First, all samples were screened using enzyme linked immunosorbent assays (ELISAs) for the presence of anti-agalsidase alfa Immunoglobulin G (IgG), Immunoglobulin A (IgA), Immunoglobulin M (IgM), and Immunoglobulin E (IgE) isotype antibodies. When a sample met the IgG, IgA, IgM, or IgE positive cut-point criteria, the appropriate ELISA was used to confirm the presence of antibodies and to determine titer. Samples confirmed with the presence of anti-agalsidase alfa IgG, IgA, IgM, or IgE antibodies were further evaluated for presence of Nab using an enzyme activity based neutralization assay. During 2014, a new test method was developed and validated at a contract research organization. The later time point samples were first screened using an ECL bridge assay. Samples screened “positive” are then confirmed by competition with agalsidase alfa in the ECL bridge format. The titer of confirmed positive samples is then determined using the same ECL bridge assay, and all confirmed positive samples are further characterized using the enzyme activity based neutralization assay.

The number and percentage of patients who become positive for any antibody isotype, each isotype, and NAb will be tabulated at baseline, at each biannual visit and overall. Shift tables of status of any antibody isotype and Nab from baseline to each biannual visit will be presented based on a classification of observations as Positive, Negative, and Not Available (NA). Both IgG and ADA data will be referred to as ADA data for the convenience of presentation. For ADA, the change in titer for antibody positive patients from baseline to each biannual visit will be summarized. These analyses will be done for the safety population overall, by cohort, and by previous ERT status.

All anti-agalsidase alfa antibody data will be listed, a listing of patients who became ADA, NAb, and IgE positive will be provided.

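### SAP 5.7.5 pools neutralising antibody status across two different confirmation steps, so for patients who straddle the November 2014 assay change an apparent NAb gain or loss can come from the assay scheme

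*SAP*

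**What the plan says.** SAP 5.7.5 says that "Anti-agalsidase alfa antibody data are obtained from 2 different testing schemes".

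- **ELISA scheme.** It records that "Anti-agalsidase alfa antibody samples collected were initially tested (prior to Nov 2014) following a tiered approach at Shire and results were reported by isotype". Confirmation on any one of four isotype assays was enough to send a sample on: "Samples confirmed with the presence of anti-agalsidase alfa IgG, IgA, IgM, or IgE antibodies were further evaluated for presence of Nab".
- **ECL scheme.** "The later time point samples were first screened using an ECL bridge assay", and reactive samples were then confirmed by competition in the same format. After that, "all confirmed positive samples are further characterized using the enzyme activity based neutralization assay". The binding method was developed and validated at a contract laboratory, whereas the ELISAs were run at the sponsor.

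The final NAb step is described in the same terms for both schemes. The documented difference is the step that decides which samples reach it.

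The same section plans the number and percentage of NAb-positive patients at baseline, at each biannual visit and overall, and also "Shift tables of status of any antibody isotype and Nab from baseline to each biannual visit will be presented". Status is Positive, Negative or Not Available. The breakdowns are overall, cohort and previous ERT status; testing scheme is not among them. SAP 5.1 defines baseline as the last valid pre-infusion result, whichever scheme produced it. The one rule that joins the schemes is a naming convention that puts IgG and ADA results under a single label, and it does not mention NAb. Sensitivity analysis (SAP 7.7) concerns outliers only.

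**The concern.** NAb status is seen only in samples that pass the binding-antibody confirmation step. If the ELISA and ECL steps pass different shares of the sera that would neutralise, the NAb-positive count changes at the switch with no change in any patient.

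A shift table from baseline to each visit is read along the axis of time on drug. For a patient whose baseline is ELISA-confirmed and whose later visits are ECL-confirmed, scheme and time on drug are confounded, and the planned table cannot separate them. A reader would take a late gain as conversion on treatment and a late loss as clearance.

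Antibodies are a named safety assessment (SAP 4.4), and NAb status also defines a subgroup (SAP 5.6.3) and a breakdown of infusion-related reactions (SAP 5.7.1).

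**Working it through.** **Plan's own figure.** The plan gives none on this point. Its one design probability, in SAP 3.6, reproduces (1 − 0.95^60 = 0.954, against a stated minimum of 95%) but has no bearing on NAb.

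**Step 1: who straddles the switch.** SAP 7.3 describes an interim set first dosed on or before 04 November 2012, so their baselines precede the switch by about two years or more. If those samples were tested on schedule, they are ELISA-confirmed, and any member still in the study afterwards contributes cross-scheme pairs. Patients enrolled after the switch, and visits tested before it, stay within one scheme.

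The documents give no enrolment curve. Assume uniform enrolment, testing at the visit date, a switch on 1 November 2014 and no dropout. The cross-scheme share of pairs is the number of enrolment months with baseline before and visit after the switch, divided by all enrolment months.

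| Assumed enrolment | Month 12 | Month 24 | Month 36 | Month 48 |
|---|---|---|---|---|
| 2011–2012 | 0/24 = 0% | 2/24 = 8% | 14/24 = 58% | 24/24 = 100% |
| 2011–2014 | 12/48 = 25% | 24/48 = 50% | 36/48 = 75% | 46/48 = 96% |

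The 8% comes from patients enrolled in November and December 2012, so almost wholly from outside the interim set. The SAP dates the ELISA scheme by when samples were tested, so stored samples could move these figures.

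**Step 2: effect on visible NAb.** Let π be the true NAb prevalence, held constant, and g1 and g2 the shares of NAb-reactive sera passing the ELISA and ECL confirmation steps. None of the three is in the documents. Count unconfirmed samples as Negative. Visible NAb is then π·g1 before the switch and π·g2 after it, and the net change is π(g2 − g1). With π = 0.20:

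| g1, g2 | Visible NAb | Net change |
|---|---|---|
| 0.80, 0.95 | 16% to 19% | +3.0 points |
| 0.60, 0.95 | 12% to 19% | +7.0 points |
| 0.95, 0.80 | 19% to 16% | −3.0 points |
| equal | unchanged | 0 |

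A net 3.0 points is 0.030 × 60 = 1.8 patients at the minimum enrolment and 0.030 × 200 = 6.0 at the maximum, if every patient straddles the switch. Other assumed values give 0.10 × (1.00 − 0.90) = 1.0 point up to 0.30 × (0.95 − 0.70) = 7.5 points.

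**Step 3: what belongs to the switch.** If a patient's two confirmation results are independent, false Negative-to-Positive shifts are π(1 − g1)g2 and false Positive-to-Negative shifts are π·g1(1 − g2).

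- Rates 0.80 then 0.95: 0.20 × 0.20 × 0.95 = 3.8% and 0.20 × 0.80 × 0.05 = 0.8%, net 3.0 points.
- Same model, ELISA at both ends at 0.80: 0.20 × 0.20 × 0.80 = 3.2% in each direction, net zero.
- Rates 0.60 then 0.95: 0.20 × 0.40 × 0.95 = 7.6% and 0.20 × 0.60 × 0.05 = 0.6%, net 7.0 points. ELISA at both ends at 0.60: 0.20 × 0.40 × 0.60 = 4.8% each way.

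Most of the gross 3.8% would therefore occur without any switch. If instead the same sera fail each time (nested steps), the false gains are π(g2 − g1) = 3.0% and 7.0%, with no false losses. Both models agree on the net figure.

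**Step 4: coding.** If unconfirmed samples are coded Not Available, the same artefact appears as NA-to-Positive or Positive-to-NA, and the percentages depend on the denominator. SAP 5.7.5 does not say which coding applies.

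**The case against.** The strongest case against runs as follows. No formal tests are planned, the SAP discloses both schemes openly, and all antibody data are listed. The NAb step carries the same description throughout. With no pass rates or concordance data, the effect may be nil. A table limited to same-scheme pairs would do harm: under 2011–2012 enrolment it would be empty from month 48.

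Much of this stands. Size and direction cannot be fixed, so a reader who infers that NAb results do move at November 2014 goes beyond the documents; they support only that the results can move. A reader might also take 3.8% or 7.6% as the effect of the switch. Those figures need independent confirmation failures and Negative coding, and the same model gives 3.2% and 4.8% in ELISA-only pairs. Nor do the documents show that the NAb assay itself changed, or that every patient is affected. The point about empty late cells is right and shapes the fix.

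What does not stand is that disclosure and listings are enough. Neither repairs a pooled shift table that will be read as conversion. No retesting of baselines, scheme breakdown or scheme-based sensitivity analysis is planned to offset it.

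**Conclusion.** The concern holds as a structural one. For patients with an ELISA-confirmed baseline and ECL-confirmed visits, the planned NAb tables cannot separate a change of confirmation step from a change in the patient.

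The attributable size is the net shift π(g2 − g1). In the illustration it is 3 points, resting on an assumed 20% prevalence, pass rates of 80% then 95%, and unconfirmed samples counted as Negative. It reverses if the rates reverse and is zero if both steps pass the same NAb-reactive sera. How many pairs are exposed depends on an enrolment pattern the documents do not give.

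The shift table for any antibody isotype, planned in the same sentence of the SAP, mixes the schemes too, and so does the NAb subgroup in SAP 5.6.3. With no formal testing and an unknown effect, this is an improvement to make because it is cheap, not a flaw that invalidates the study.

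**What to change.** In SAP 5.7.5:

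1. Keep the planned baseline-to-visit NAb shift table, but present it by scheme pair: ELISA–ELISA, ECL–ECL and ELISA–ECL. Label the cross-scheme stratum as not interpretable as conversion on its own.
2. Show by-visit NAb percentages by scheme, each with the number of samples actually tested for NAb.
3. State whether a sample that is not confirmed for binding antibody is coded NAb Negative or Not Available.
4. For patients who cross the switch, add a supplementary within-ECL shift from the first ECL sample, labelled as not a shift from baseline. It starts after treatment has begun and cannot show conversion before that sample.
5. Apply the same scheme split to the shift table for any antibody isotype.

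The cost is SAP wording and table programming, with no new patient data; the scheme should be identifiable from the test records. The downside is smaller strata, with few or no same-scheme pairs at late visits for early enrollees. For that reason the cross-scheme stratum should be kept and labelled, not dropped.

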5.6.3 Subset Analyses

Although no subgroup analysis is explicitly indicated in the study protocol, subgroup analyses by sex group, age group, previous ERT status, anti-drug antibody (ADA) status and neutralizing antibody (NAb) status will be performed, as applicable. Subgroups of age group, previous ERT status, ADA status and NAb status are defined as:

Age group (years) is defined as:

- <18
- ≥18

Previous ERT status is defined as:

- Previously on Fabrazyme (switched)
- Previously on RB Replagal
- Treatment-Naïve
- Other (including the patients who were previously on Fabrazyme and Replagal, on Replagal RB and Replagal AF, and whose ERT status is unknown)

ADA status is defined as:

- Positive: At least one positive test for ADA during the study evaluation period
- Negative: No positive test for ADA during the study evaluation period

NAb status is defined as:

- Positive: At least one positive test for NAb during the study evaluation period
- Negative: No positive test for NAb during the study evaluation period

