The number and percentage of patients reporting IRRs will be tabulated for any IRR, and by SOC and PT by cohort, previous SRT status, age group, sex and overall based on the safety population. IRRs by SOC and PT will be tabulated by severity and cohort, by serious and cohort, and by closest relationship. In addition, the number and percentage of patients with at least one, and no IRRs will be tabulated by anti-drug antibody (ADA) status and neutralizing antibody (NAb) status status.

The number and percentage of patients reporting SAEs will be tabulated for any SAE, and by SOC and PT by cohort, previous SRT status, age group, sex and overall based on the safety population. In addition, SAEs by SOC and PT will be tabulated by severity and relationship by cohort, separately.

The number and percentage of patients reporting TEAEs that led to permanent discontinuation will be tabulated for any TEAE, and by SOC and PT by cohort, previous ERT status, age groups and overall.

Separate data listings will be presented showing all SAEs, deaths, and TEAEs leading to treatment discontinuation.

All AEs will be listed by patient for the safety population and those AEs considered to be treatment-emergent, as well as IRRs will be flagged as such.

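### For ELISA-tested samples the SAP's ADA status is most naturally read as IgG only, so patients positive solely for IgA, IgM or IgE, and never ECL-positive, count as ADA-negative in the infusion-reaction table

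*SAP*

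**What the plan says.** SAP 5.7.5 sets out two testing schemes. Before November 2014, samples were tested "following a tiered approach at Shire and results were reported by isotype", with separate ELISAs for IgG, IgA, IgM and IgE. NAb testing in that period did not depend on IgG: "Samples confirmed with the presence of anti-agalsidase alfa IgG, IgA, IgM, or IgE antibodies were further evaluated for presence of Nab". After the change, "The later time point samples were first screened using an ECL bridge assay", followed by confirmation, titer and NAb testing of confirmed positives. No isotype result is described for this assay.

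The same section then sets the naming rule: "Both IgG and ADA data will be referred to as ADA data for the convenience of presentation". It also plans a listing that names ADA, NAb and IgE as three separate items.

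SAP 5.6.3 turns test results into a patient-level status. The two ADA categories are "Positive: At least one positive test for ADA during the study evaluation period" and "Negative: No positive test for ADA during the study evaluation period". NAb status is defined separately, with "Positive: At least one positive test for NAb during the study evaluation period". No category is provided for a patient positive only for an isotype other than IgG.

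SAP 5.7.1 uses these statuses for infusion-related reactions: patients with at least one and with "no IRRs will be tabulated by anti-drug antibody (ADA) status", and likewise by NAb status.

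**The concern.** The label ADA appears to change meaning with the date of testing. If ELISA-period ADA is IgG alone, some patients with a confirmed anti-agalsidase alfa antibody, including some with IgE, become part of the antibody-negative comparison group. Any reactions they have are then reported as reactions in ADA-negative patients.

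Safety is the study's only objective, and the IRR-by-antibody tabulation is where a reader will look for a link between immunogenicity and infusion reactions. The report could also look inconsistent: one patient could be positive in the any-isotype table, negative for ADA in the IRR table, and positive for NAb.

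**Working it through.** The documents give no antibody rates, so there is no plan figure on this point to reproduce. The SAP's one design figure (section 3.6) does reproduce, 1 − 0.95^60 = 0.954 against the stated 95%, but nothing here depends on it.

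**Step 1. Which ELISA results count as ADA-positive.** With four isotypes there are 2^4 − 1 = 15 possible non-empty patterns of confirmed positivity.
- Patterns that include IgG: 2^3 = 8. These are ADA-positive under the 5.7.5 rule.
- Patterns without IgG: 2^3 − 1 = 7. These supply no positive ADA test.
- Patterns that qualify for NAb testing: all 15, because any confirmed isotype was enough.

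ADA-negative with NAb-positive is therefore possible in 7 of the 15 patterns. This counts patterns and says nothing about how many patients have them.

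**Step 2. Which patients are affected.** Status under 5.6.3 rests on at least one positive test over the whole study. A patient with a non-IgG isotype is still ADA-positive if any ELISA sample was IgG-positive or any later sample was positive by ECL. The affected group is therefore patients positive only for IgA, IgM and/or IgE by ELISA and never positive by ECL. Patients with no ECL-tested sample, such as any who left before the change of assay, cannot be picked up by a later ECL result.

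**Step 3. How many that could be (assumed rates).** If 1% to 10% of patients are in the affected group:
- of 60 patients (the minimum): 60 × 0.01 = 0.6 to 60 × 0.10 = 6
- of 200 patients (the maximum): 200 × 0.01 = 2 to 200 × 0.10 = 20

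**Step 4. What it could do to the IRR contrast (assumed counts).** Take 60 ELISA-tested patients: 15 IgG-positive, 6 of them with an IRR, and 45 IgG-negative, 6 of them with an IRR. Suppose 3 of the 45 are positive for a non-IgG isotype, and k of those 3 had an IRR.

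With ADA read as IgG: 6/15 = 40% against 6/45 = 13.3%, ratio 3.0.

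With any-isotype status: (6 + k)/18 against (6 − k)/42.

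| k | ADA-positive | ADA-negative | Ratio |
|---|---|---|---|
| 0 | 6/18 = 33.3% | 6/42 = 14.3% | 2.3 |
| 1 | 7/18 = 38.9% | 5/42 = 11.9% | 3.3 |
| 2 | 8/18 = 44.4% | 4/42 = 9.5% | 4.7 |
| 3 | 9/18 = 50.0% | 3/42 = 7.1% | 7.0 |

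The ratio can move either way from 3.0, depending on whether the reclassified patients reacted. If no patient is positive for a non-IgG isotype alone, nothing changes.

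**The case against.** The strongest reply is that the 5.7.5 sentence is a naming convention placed just before the titer summary, not a definition of status. The SAP's abbreviation list gives ADA its general meaning of anti-drug antibody, section 5.6.3 does not equate it with IgG, and no sentence says outright that IgA, IgM or IgE are left out. This stands to the extent that the IgG reading is an inference. It remains the natural one: the sentence pairs IgG, and no other isotype, with ADA, and the planned listing treats IgE as something other than ADA. If the sponsor meant otherwise, two programmers could still build different variables from the same text.

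The second reply is that much is already planned. SAP 5.7.5 tabulates any-isotype and each-isotype positivity, gives shift tables for any-isotype status, lists IgE-positive patients and lists all antibody data. SAP 5.7.1 flags IRRs in the AE listing. All of this stands, and affected patients can be traced by hand, but no planned table crosses any-isotype status with IRRs.

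A reader might draw four stronger conclusions that the documents do not support:
- That every IgA-, IgM- or IgE-positive patient is classed ADA-negative. One IgG-positive or ECL-positive sample at any time makes the patient ADA-positive.
- That IRR by ADA status is the only planned link between antibodies and reactions. The same sentence of 5.7.1 also tabulates IRRs by NAb status, which does not depend on the ADA label.
- That an ADA-negative, NAb-positive patient breaks the tiered testing scheme. The scheme sent any confirmed isotype to NAb testing, so the combination follows from it; the oddity lies in the label.
- That the ECL assay is known to detect all isotypes. The SAP does not say which isotypes it detects. That it is not isotype-specific is inferred from the bridge format and the absence of isotype results.

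**Conclusion.** The point holds for a limited group. Following the SAP on its natural reading, patients confirmed positive only for IgA, IgM and/or IgE by ELISA, and never positive for IgG or by ECL, are counted as ADA-negative in the IRR table and may be NAb-positive.

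The size is unknown because the documents report no isotype rates. The assumed range of 1% to 10% gives 0.6 to 6 of 60 patients, or 2 to 20 of 200. The direction is also unknown: in the illustration the ratio of 3.0 becomes anything from 2.3 to 7.0, and a reader should not infer that the plan necessarily understates an association. The study is descriptive, so no test, error rate or sample size is affected, and the documents attach no decision rule to ADA status. The correction is still worth making, because it removes an avoidable ambiguity from a safety contrast using data already collected.

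**What to change.** In SAP 5.6.3 and 5.7.5, define ADA status as positive if any of IgG, IgA, IgM or IgE is confirmed positive by ELISA, or if the ECL result is confirmed positive. Use this status for the ADA subgroup and the IRR-by-ADA table. Keep IgG alone only for the ELISA titer summaries, and label those as IgG titer.

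The cost is a short change of wording and one derived variable from results already held; no new testing is needed. The definition should be written into the SAP itself, because section 5.1 allows further derived variables to be added without an amendment. Reported ADA prevalence may rise slightly. The change makes the ELISA-period status consistent with the rule that triggered NAb testing, but does not by itself make the two assays equivalent, and the clinical study report should say so.

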4.4 Safety Assessments

Safety and tolerability will be assessed by AE reporting, changes in vital signs (from immediately before to immediately after every infusion), and changes from screening assessments to biannual visits in physical examination, blood tests, and anti-agalsidase alfa antibodies (in serum).

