5 STATISTICAL ANALYSIS

5.1 General Methodology

All analysis will be performed by the Biometrics Department, Shire HGT using SAS[®] Software version 9.3 or higher (SAS institute, Cary, NC, USA). All study data will be presented in by-patient data listings.

No formal statistical tests will be conducted. Tabular summaries of patient baseline demographic and clinical characteristics, patient disposition, medical history, vital signs, AEs, anti-agalsidase alfa antibody, and infusion information will be produced for the safety population. The safety population includes all patients who receive at least one full or partial infusion of Replagal. Continuous data collected prior to receiving study drug and at subsequent visits will be summarized using descriptive statistics (n, mean, median, minimum, maximum, and standard deviation). Categorical data will be summarized as frequencies and percentages. All data summaries will be presented for each cohort and overall, as appropriate, unless otherwise indicated

Cohort:

Cohort is defined as:

- Cohort 1: Patients from CFDI and receiving Replagal on EOW regimen
- Cohort 2: Patients who participated in REP001a and receiving Replagal on weekly regimen

Data Derivations:

The following key derived and computed variables have been initially identified. It is expected that additional variables may be required. The SAP will not be amended for additional variables. All derived and computed variables, including additional variables later identified, will be documented in the “Define Document,” and also in the SAS analysis dataset creation programs. The following are anticipated data derivations:

- *Screening period:* Within 6 months prior to first dose
- *Pre-treatment period:* Prior to first study drug infusion
- *Day 1:* Day of first study drug infusion
- *Date of Enrollment (entry):* Date informed consent is signed
- *Baseline:* Last valid non-missing assessment made prior to the first study drug infusion.
- *Change from Baseline:* Post-baseline value – Baseline Value

- *% Change from Baseline:* $\{(Change\ from\ Baseline / Baseline) * 100\}$
- *Change from Pre-infusion:* Value immediately after infusion – value immediately before infusion.
- *% Change from Pre-infusion:* $\{(Change\ from\ pre-infusion / pre-infusion) * 100\}$
- *Age:* integer of $\{(date\ of\ informed\ consent - date\ of\ birth) / 365.25\}$
- *Duration of study drug exposure:* (Date of last infusion – date of first infusion)+1

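### Change in antibody titre from baseline carries no same-assay condition, so patients with an ELISA baseline and an ECL visit have titres from two assays subtracted

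*SAP*

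**What the plan says.** SAP 5.7.5 explains that the antibody data come from two testing schemes. Samples tested before November 2014 went through isotype ELISAs (IgG, IgA, IgM, IgE) at the sponsor, where "the appropriate ELISA was used to confirm the presence of antibodies and to determine titer". Later samples went to an ECL bridge assay at a contract research organization: "The titer of confirmed positive samples is then determined using the same ECL bridge assay". There, the word same refers to the assay that screened and confirmed the sample, not to the assay used for the patient's baseline.

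The section then merges the two sources: "Both IgG and ADA data will be referred to as ADA data for the convenience of presentation". On that merged variable it plans the titre analysis: "For ADA, the change in titer for antibody positive patients from baseline to each biannual visit will be summarized". The strata are overall, cohort and previous ERT status.

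The derivations are in SAP 5.1. Baseline is "Last valid non-missing assessment made prior to the first study drug infusion" and change is "Post-baseline value – Baseline Value". Neither mentions the assay. The only sensitivity analysis, in SAP 7.7, concerns outliers. Protocol 7.4 plans summaries of antibody and neutralizing-antibody status and has no assay rule either.

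**The concern.** A titre is read on the scale of the assay that produced it. An isotype-specific ELISA and a bridging ECL assay need not give the same number for the same serum, and nothing in the documents says that these two do. Followed literally, the SAP subtracts one from the other whenever a patient's baseline and visit fall on opposite sides of the switch, and one by-visit row can mix such pairs with same-assay pairs.

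SAP 4.4 lists change in serum antibodies from screening to the biannual visits among the safety assessments. A reader who sees titres rise or fall in the pooled table could not tell immunogenicity from a change of laboratory method.

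Two related gaps have the same cause:

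- **Isotype tables.** The SAP tabulates each isotype and shifts in the status of any isotype, but describes no isotype for ECL results. It does not say whether an ECL result counts as Positive, Negative or Not Available.
- **Neutralizing antibodies.** Only samples confirmed positive for binding antibody go on to this test; for the ECL scheme, "all confirmed positive samples are further characterized using the enzyme activity based neutralization assay". Because the confirming assay changed, NAb status also depends on the scheme. ADA and NAb status in turn define the subgroups of SAP 5.6.3 and the infusion-reaction tabulation in 5.7.1.

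**Working it through.** The plan gives no figure for titre or for agreement between the assays, so there is none to reproduce. The check has three parts.

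**1. Do crossing pairs arise?** SAP 7.3 says the interim set was first dosed on or before 04 November 2012, so its pre-dose samples were collected before the ECL method was developed in 2014. The final analysis waits until the last patient completes. Any of these patients still on study after the switch therefore has later samples in the ECL period. Crossing pairs are to be expected.

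**2. At which visits?**

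Inputs and assumptions:
- Switch S = 01 Nov 2014, from SAP 5.7.5. The SAP dates testing, so collection date is used as a stand-in for test date.
- First dose D is no earlier than 30 Sep 2010, the original protocol date. This is a bound, not a documented first dose.
- Baseline sample date B lies between D minus 6 months and D.
- Month m counts from first dose.

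A pair at month m crosses if B < S and D + m ≥ S. An ELISA–ELISA pair needs D + m < S.

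| Month m | First doses before S whose pair crosses | ELISA–ELISA pair possible for |
|---|---|---|
| 6 | May–Oct 2014 | D before May 2014 |
| 12 | Nov 2013–Oct 2014 | D before Nov 2013 |
| 24 | Nov 2012–Oct 2014 | D before Nov 2012 |
| 36 | Nov 2011–Oct 2014 | D before Nov 2011 |
| 48 | Nov 2010–Oct 2014 | D from 30 Sep to 31 Oct 2010 only |
| 54 and later | all D before Nov 2014 | none (30 Sep 2010 + 54 months = 30 Mar 2015) |

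First doses from Nov 2014 to Apr 2015 can also cross, at any visit, because baseline serum may have been drawn up to 6 months earlier and so before S. Crossing is thus possible at early and late visits alike. From month 54, a row can hold only cross-assay and ECL–ECL pairs. These windows are approximate.

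**3. What would a crossing pair show?** Illustration only. Assume no real change, a positive titre T at baseline, and ECL titre = k × ELISA titre, with k from 0.1 to 10. The documents do not give k.

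- Change by SAP 5.1 = kT − T = (k − 1)T. For k = 0.1 this is −0.9T; for k = 1, 0; for k = 10, +9T.
- If 25% of a row's pairs cross (assumed, equal baseline titres), the row mean moves by 0.25 × (k − 1)T: −0.225T, 0 and +2.25T.
- The asymmetry comes from the raw scale. On log2, a crossing pair shows log2(k) = −3.32, 0 and +3.32, and 25% crossing moves the mean by −0.83, 0 and +0.83.
- In this set-up the row median stays at 0 while fewer than half the pairs cross, but the minimum (k < 1) or maximum (k > 1) takes the full artefact.

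The artefact vanishes only if k = 1 or if no pair crosses.

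**The case against.** The strongest reply is that no harm has been shown. The documents give neither the relation between the assays nor a count of affected pairs, and the illustrative figures depend on an assumed k, an assumed share and the raw scale. That stands: high confidence applies to the missing rule, not to the size of its effect. The illustration also covers only patients with a titre at both time points, and the SAP does not say how a negative baseline enters the summary.

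The second reply is about weight. The study is descriptive, no formal tests are planned, Protocol 7.4 asks only for antibody status, the interim endpoint in SAP 7.3 was antibody status, and no documented decision depends on titre change. This also stands, and it limits the severity.

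The third is that the SAP is open about both schemes, that the shared name may be a label only, and that all antibody data are listed. This helps less. The sentence after the labelling rule computes titre change on the merged variable, and no analysis by assay is specified. A listing does not correct a summary table. The SAP does not promise an assay column, although isotype-level entries might let a reader infer the scheme.

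Finally, SAP 5.1 lets further derived variables be documented outside the SAP, so programmers could add an assay flag. A flag is not a rule on which pairs to summarise.

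**Conclusion.** The concern holds. As written, SAP 5.7.5 with the definitions in 5.1 produces ECL-minus-ELISA differences for every antibody-positive patient whose pair straddles the switch, and pools them with same-assay differences. This follows from the stated rules and is more than a missing detail. Same-assay pairs are not affected.

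The size, direction and number of affected pairs cannot be derived from the documents. The claim that pairs will cross rests on the dates in SAP 7.3 and on there being patients still under observation after the switch; the month-by-month windows also rest on collection date standing in for test date. The trial's overall safety conclusions do not hinge on this table, but it belongs to a named safety assessment and should be corrected before the final analysis.

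**What to change.** Amend SAP 5.7.5, with matching wording elsewhere:

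1. Record the assay on every antibody result and show it in the listings.
2. Summarise change in titre only where baseline and visit used the same assay. For cross-assay pairs, give their number and the observed titres at each time point by assay, without a difference and without pooling. State the scale (raw or log) and how a negative baseline is handled.
3. Present ADA and NAb status and shift tables by assay, and state how an ECL result is classified in the any-isotype shift table.
4. Restrict the percentages for each isotype to ELISA-tested samples.
5. Keep the SAP's meaning of ADA (ELISA IgG or ECL) and state it explicitly in 5.6.3 and 5.7.1.

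This takes SAP text and a programming flag; no new samples are needed. The artefact in the change summary is then zero by construction.

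The price is more than smaller cells. Under the timing assumptions above, patients with an ELISA baseline have no same-assay pair from month 54 onward, so they leave the long-term change summary and there is no single long-term titre curve. If the sponsor wants to keep one, the SAP would have to document a retest of stored baseline serum by ECL or a bridging of the two scales. The documents do not say whether either is available.
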